10.2 Secondary study parameters

In the secondary analysis, the multivariable linear regression model analysis from the primary analysis will be used to identify independent variables (age, change in body weight, subjected to ketogenic diet and oral contraceptive use at baseline) as predictors of the primary endpoint. An additional analysis will be performed including adherence to the diet as independent variable.

Analysis for adherence to the ketogenic diet will be done via descriptive statistics. Adherence to the diet will be calculated as a percentage.

Side effects of the ketogenic diet will be analyzed via descriptive statistics. Occurrence of side effects will be given as a percentage.

Results of the prediction model/chance assessment tool (30), providing the estimated chance (%) of HCA regression to 0,5 cm at 1 and 2 years after diagnosis will be compared between our intervention group and the matched historical controls by the Chi-square test.

Change in liver fat content (%) will be compared in our intervention group by a multivariable linear regression model. The independent variables in this model will include age, change in body weight and oral contraceptive use at baseline. An additional analysis will be performed including adherence to the diet as independent variable.

Changes in plasma parameters will be compared in our intervention group by using descriptive statistics, t-test in the case of continuous outcome variables with normal distribution or non-parametric test in the case of non-normality. The Chi-square test will be used for categorical data.

Change in quality of life will be compared over time in our intervention group by a mixed-effects model analysis, taking repeated measurements into account. The independent variables in this model will include age and change in body weight. An additional analysis will be performed including adherence to the diet as independent variable.

Mean change in body weight, change in body composition and resting energy expenditure will be estimated in our intervention group by a mixed-effects model analysis, taking repeated measurements into account. The independent variables in this model will include age and sex. An additional analysis will be performed including adherence to the diet as independent variable.

Subpopulation: the same models will be constructed, but the models will not be adjusted for oral contraceptive use at baseline. This subgroup will also have no results of the prediction model/chance assessment tool and therefore this cannot be computed in the subpopulation.

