Nature and extent of the burden and risks associated with participation, benefit and group relatedness: The extent of the burden of our study is considered low. Dietary restriction and the ketogenic diet have been proven feasible and safe in previous studies. For this study, three extra blood samples by 3 venous punctures are taken. No extra visits to the hospital or imaging studies are needed in order to obtain all the information required for this study. Several standardized questionnaires are asked to be filled in during and after the diet. Mentioned questionnaires take about 10 minutes to complete. No other risks concerning the dietary intervention are to be expected.

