2. OBJECTIVES

Primary Objective: to determine the effect of a moderate calorie restricted, ketogenic diet on the reduction in size of hepatocellular adenoma after 6 months in adult female patients.

Secondary Objectives:

- To determine the feasibility / adherence to the ketogenic diet
- To identify predictors of the primary endpoint
- To assess possible change in the estimated chance of HCA regression to 0,5 cm at 1-2 years due to the ketogenic diet, estimated by prediction model.
- To determine the change in liver fat content
- To investigate potential side effects & burden of diet
- To determine the effect on Quality of Life (QoL)
- To assess change in body weight and plasma parameters
- To investigate the effect of the diet on change in body composition and resting energy expenditure

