8.1.2 Secondary study parameters/endpoints

- Feasibility / Adherence to the ketogenic diet
 - o Self-reported adherence, measured via in-house used questionnaire “Ketodieet”. Questionnaire has not validated but partly based on “Vragenlijst Intensive Monitoring Lareb (65)”, measures the amount of days subjects did not use the ketogenic diet. Serves as a tool during outpatient clinic visits to the dietician.
 - o Ketone levels in urine, self-measured thrice weekly by urine strips (Siemens, Multi stix 10SG)
 - o Ketone levels, measured at physical meetings with dietician, by Ketosemeter CareSense Dual
- Side effects & burden of diet, measured via in-house used questionnaire “Ketodieet”. Questionnaire has not validated but partly based on “Vragenlijst Intensive Monitoring Lareb (65)”, measures possible side effects mentioned by subjects during the use of the ketogenic diet. Serves as a tool during outpatient clinic visits to the dietician.
- Results of the prediction model/chance assessment tool (30), providing the estimated chance (%) of HCA regression to 0,5 cm at 1 and 2 years after diagnosis.
- Change in Liver fat content, measured on MRI
- Change in plasma parameters:
Fasting glucose, fasting insulin, HbA1c, total cholesterol, HDL-cholesterol, LDL-cholesterol, free fatty acids, triglycerides levels, branched amino acids, IGF -1, Growth hormone (hGH), β -Hydroxybutyrate
- Quality of life measured by RAND-36 (66-69), Dutch version 2, 2012. Higher score meaning higher QoL
- Change in body weight (kg)
- Change in body composition (fat mass / fat free mass)
 - o via Bio-electrical Impedance Analysis (Bodystat quadscan 4000, Euromedix, Leuven, Belgium)
- Resting Energy Expenditure
 - o Via Quark RMR, Cosmed Benelux B.V., Nieuwegein, The Netherlands

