8.2 Randomisation, blinding and treatment allocation

All subjects in our study will be allocated to the dietary intervention and henceforth cannot be blinded.

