This consult will focus on explaining the study diet, nutritional assessment, adherence to the diet, measurements, advice and instruction in case of possible side effects.

Nutritional assessment

Nutritional assessment will take place during the study visits at the outpatient clinic and consists of:

- Resting energy expenditure (Indirect calorimetry)
- Body composition by bioelectrical impedance analysis (BIA)
- 3-day food diary filled in at home and cross checked during the study visits.
- Anthropometric measurements, body weight will be measured during visits to the outpatient clinic.

Nutritional assessment is part of standard dietetic care. For the operational procedures we refer to the NAP website (72). The procedure involves measurement of inspired and expired air. Participants are asked to lay down in a supine position for approximately half an hour and to breath in and out of a ventilated hood. Bio impedance involves the patient to lay down in a supine position or stand on a special scale with special handgrips for 1 minute.

Questionnaires

Questionnaires will focus on adherence and any possible side effects / symptoms subjects might experience during the ketogenic diet. Other questionnaires conducted during study focus on quality of life and physical activity.

Consultation by Clinician / Investigator

This consult will focus on any possible abdominal pain / complaints, any complaints after halting oral contraceptives, advice to currently avoid pregnancy and advice concerning when to contact our outpatient clinic.

Imaging studies

Subjects will receive their follow-up MRI according to normal treatment protocol after 6 months. No additional imaging studies will be performed for this study, extra measurements will be made on already acquired imaging studies to calculate the liver fat content.

Laboratory testing

Blood will be acquired by venous puncture for measuring fasting parameters. Blood sampling will be done thrice, each time 2 tubes of 10ml will be withdrawn.

Urine testing

Ketones / Acetoacetate in urine will be assessed thrice weekly by subjects themselves using a simple urinestrip to determine / confirm ketose state and therefore adherence. Subjects will be carefully instructed during their clinical appointments on how to use these strips.

Followup overview:

Table 2: Study overview, window for appointments: T₁&T₂: +/- 3 days, T₃-T₅: +/- 1 week

Procedure	T ₀ Baseline	T ₁ 2 weeks	T ₂ 6 weeks	T ₃ 3 months	T ₄ 4 months	T ₅ 6 months

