Dietary restriction	Start diet (Phase 1)			Start diet (Phase 2)		End of diet
Informed Consent	X					
Type of contact	Physical	Telephone	Telephone	Physical	Telephone	Physical
Consultation by Dietician	Outpatient clinic	By phone	By phone	Outpatient clinic	By phone	Outpatient clinic
Consultation by Clinician / investigator	Outpatient clinic					Outpatient clinic
MRI-Followup						X
Laboratory testing	X			X		X
Anthropometric measurements	X			X		X
Nutritional assessment:	X			X		X
Questionnaires:						
IPAQ:	X			X		X
Rand-36:	X			X		X
Food Diary:	X	X	X	X	X	X
Side effects:		X	X	X	X	X

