9.2 AEs, SAEs and SUSARs

9.2.1 Adverse events (AEs)

Adverse events are defined as any undesirable experience occurring to a subject during the study, whether or not considered related to ketogenic diet. All adverse events reported spontaneously by the subject or observed by the investigator or his staff will be recorded. When adverse or serious adverse events are observed, the principal investigator will be informed. Subsequently, the principal investigator takes responsibility for the correct processing of the events.

Known minor side effects of the ketogenic diets (constipation, diarrhoea, nausea and/or vomiting) will be analysed separately and are therefore not considered an adverse effect.

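### Symptoms are not recorded before the diet starts, so the side-effect percentage may include complaints the women already had

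*Protocol*

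**What the plan says.** Section 2 lists as a secondary objective: "To investigate potential side effects & burden of diet". Section 8.1.2 measures it with the in-house Ketodieet questionnaire, described as not validated, which "measures possible side effects mentioned by subjects during the use of the ketogenic diet".

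In the study overview table of section 8.3, the T0 entry in the diet row begins "Start diet (Phase 1". IPAQ, RAND-36 and the food diary are all marked at T0. The side-effects row is marked at T1 (2 weeks), T2, T3, T4 and T5, and its T0 cell is empty.

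Section 8.2 excludes a concurrent comparator: "All subjects in our study will be allocated to the dietary intervention and henceforth cannot be blinded". Section 10.2 analyses side effects with descriptive statistics: "Occurrence of side effects will be given as a percentage". Section 9.2.1 names constipation, diarrhoea, nausea and vomiting as known minor side effects of the diet, which "will be analysed separately and are therefore not considered an adverse effect".

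**The concern.** The named complaints are not specific to a ketogenic diet, and some women will have them beforehand. A percentage presented as side effects of the diet needs a reference, either a pre-diet value or a comparison group. Here the first questionnaire comes after about two weeks on diet, every participant follows the diet, and section 3 mentions no symptom data for the historical controls.

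The figure matters somewhat more than its descriptive status suggests. Section 9.2.1 takes the common gastrointestinal complaints out of adverse-event reporting, so this questionnaire is the only instrument the protocol schedules for them. A reader judging tolerability will rely on this percentage, which may be too high by an amount that the collected data cannot reveal. Nor can a statistical analysis plan repair this later: the visit schedule is fixed in the protocol, and a T0 value that was not collected cannot be recovered.

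**Working it through.** The protocol states no side-effect rate, so there is no figure to reproduce. The check has two parts.

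**Schedule (study overview table, section 8.3)**

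| Item | T0 | T1 | T2 | T3 | T4 | T5 |
|---|---|---|---|---|---|---|
| Diet | start | | | phase 2 | | end |
| IPAQ, RAND-36 | X | | | X | | X |
| Food diary | X | X | X | X | X | X |
| Side effects | – | X | X | X | X | X |
| Clinician consultation | yes | | | | | yes |

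The side-effects row has five entries against six in the food-diary row, and the missing one is the pre-diet visit. Quality of life, body weight and plasma parameters are also studied only within the intervention group, but they have a T0 value and section 10.2 analyses their change.

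**Illustration of the consequence**

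Inputs, all assumed because the documents give none:
- *d*: proportion with a diet-caused complaint, set at 20%.
- *b*: proportion with a background complaint, varied from 0% to 30%.
- The two are independent, and every background complaint is recorded as a side effect (full attribution).

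Reported proportion = 1 − (1 − d)(1 − b). Overstatement = reported − d = b(1 − d).

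| b | Reported | Overstatement (points) |
|---|---|---|
| 0% | 1 − 0.8 × 1.0 = 20% | 0 |
| 10% | 1 − 0.8 × 0.9 = 28% | 8 |
| 20% | 1 − 0.8 × 0.8 = 36% | 16 |
| 30% | 1 − 0.8 × 0.7 = 44% | 24 |

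If only a fraction *a* of background complaints is recorded as side effects, b is replaced by a × b and the overstatement becomes a × b × (1 − d). It falls to zero if the form screens out earlier complaints completely.

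The same report can also arise from different truths. With full attribution, 20% (about 10 of the 51 women required in section 4.4) results from d = 20% with b = 0%, and equally from d = 0% with b = 20%. Likewise 28% (about 14 of 51) results from d = 20% with b = 10%, and from d = 10% with b = 20%. The planned percentage cannot distinguish the members of either pair.

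**The case against.** **Every complaint will be counted as a diet effect.** A reader might infer this from the empty T0 cell, but the documents do not support it. The form is not reproduced. It may ask about onset or relation to the diet, and a form of that kind is naturally given only on diet. Only the weaker statement stands: earlier complaints may be counted. Any screening would rest on unblinded recall in a questionnaire that is not validated.

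**The T0 visit already covers this.** It does in part. The clinician consultation takes place at T0 and covers abdominal complaints and "any complaints after halting oral contraceptives". Section 8.1.3 also collects comorbidities and medication at baseline. But none of this is the same instrument, and nothing in section 10 uses it for the side-effect percentage.

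**A T0 form would also remove complaints from stopping contraceptives.** It would not. Those beginning after T0 would count as new and stay mixed with diet effects. The protocol gives no cessation date relative to T0. The matter concerns mainly the main study population, because the subpopulation received the cessation advice in its earlier surveillance period (section 4.1).

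**Pain from the adenoma inflates the figure.** The documents do not show this: abdominal pain is not among the minor side effects in section 9.2.1, and the questionnaire items are not shown.

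**The Summary confirms that no questionnaire precedes the diet.** It says: "Several standardized questionnaires are asked to be filled in during and after the diet". That sentence is weak evidence. It speaks of standardized forms, whereas Ketodieet is in-house, and the overview table does schedule IPAQ and RAND-36 at T0. The table is what carries the point.

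**The endpoint is only descriptive, and the error runs in the cautious direction.** Both parts are fair. No test or comparison of side effects is planned, and overstating them does not flatter the diet's safety. This limits the weight of the point, but the figure for a stated objective would still be hard to interpret.

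**Conclusion.** The point holds as a minor one. The schedule facts are certain: the side-effect questionnaire has no T0 assessment, there is no concurrent control, and section 10.2 plans only a crude percentage. The consequence is possible rather than shown: complaints present before the diet may be reported as its side effects.

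The amount is unknown. The range of 0 to 24 percentage points rests on an assumed diet-caused rate of 20%, assumed background rates of 0% to 30%, independence and full attribution. It illustrates the problem and does not estimate the trial's error. One descriptive secondary endpoint is concerned; the primary endpoint is not affected.

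**What to change.** 1. In the study overview table of section 8.3, add an entry at T0 in the side-effects row, with the symptom items of the Ketodieet questionnaire completed before the diet starts.
2. In section 10.2, report at each visit the percentage of women with complaints that are new or worsened since T0, beside the crude percentage. If the form does not record severity, it needs to do so for worsening to be seen.
3. Add a sentence stating that complaints beginning after T0 from stopping oral contraceptives, mainly in the main study population, cannot be separated from diet effects without a concurrent control.

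The cost is one short form at a physical visit where other questionnaires are already completed, one table entry and a few sentences. No extra visit is needed. The change addresses complaints present at T0; unrelated complaints that begin later would still be included, which is why the limitation should be stated.

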4.4 Sample size calculation

We based our sample size calculations on the large multicentre retrospective cohort mentioned earlier study (30). This study calculated a median (IQR) HCA diameter at baseline of 82.0mm (65-100) and at 6-month follow-up of 65.0mm (56-80).

Based on this, considering a relevant effect of 20% difference in mean tumour size after 6 months, we estimated an average additional decrease of 13mm in the intervention group when compared to our earlier collected (30).

With a two-sided alpha set at 0.05, power at 0.95, we calculated that at least 51 subjects are required. Anticipating +/- 10% drop-out, we aim to include 55 participants in this study. We aim to include all study subjects in 1 – 1,5 years.

Since the subpopulation is a pilot study, we did not perform a sample size calculation. For this subpopulation, we hypothesized a sample size of 20 subjects. We estimated that this sample size is large enough to provide a reliable initial answer.

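### The liver fat change model omits baseline liver fat, which probably costs precision and leaves the adherence and weight-change coefficients open to confounding

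*Protocol*

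**What the plan says.** Protocol section 8.1.2 lists as a secondary endpoint "Change in Liver fat content, measured on MRI". Section 8.3 (imaging studies) says that no scans are added and that "extra measurements will be made on already acquired imaging studies to calculate the liver fat content".

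Section 10.2 gives the analysis: "Change in liver fat content (%) will be compared in our intervention group by a multivariable linear regression model". The covariates follow: "The independent variables in this model will include age, change in body weight and oral contraceptive use at baseline". Then: "An additional analysis will be performed including adherence to the diet as independent variable". Earlier in the same section, "Adherence to the diet will be calculated as a percentage".

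The subpopulation paragraph at the end of section 10.2 keeps the same models and only drops contraceptive use. Baseline liver fat is not named as a covariate for this outcome anywhere in the protocol, and it is not among the baseline characteristics listed in section 8.1.3.

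Section 8.2 states that "All subjects in our study will be allocated to the dietary intervention and henceforth cannot be blinded". Adherence therefore varies within one treated group and is not assigned.

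**The concern.** The outcome is follow-up fat minus starting fat, so it is tied arithmetically to the starting value. If change is counted in percentage points, a woman who starts at 4% can lose at most 4 points, while one who starts at 20% can lose far more. Entry requires BMI above 25 and sets no limit on liver fat, so the design does not restrict the starting value.

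Two things are at stake.

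- **Precision.** Variation in change that starting fat would explain stays in the residual and widens the interval for every coefficient of interest.
- **Possible confounding.** If women with more liver fat at the start follow the diet better or worse, or lose more or less weight, the adherence and weight-change coefficients partly reflect how much fat there was to lose. The model has only the diet group, so neither randomisation nor the matching to historical controls protects against this.

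Section 10 applies a two-sided 0.05 level to secondary analyses unless stated otherwise, so these coefficients are likely to be tested and interpreted.

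**Working it through.** **The plan's own figure.** There is none for this model. The only sample size statement is "With a two-sided alpha set at 0.05, power at 0.95, we calculated that at least 51 subjects are required", which concerns tumour diameter. It can be reproduced closely. The follow-up IQR of 56 to 80 mm gives SD = 24/1.349 = 17.8 mm. With a 13 mm difference, this needs 49 (normal approximation) or 50 (t) per group; with SD 18 mm it needs 50 or 51. Below, 51 serves only as the approximate size of the diet group.

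**Inputs not in the protocol (assumptions).** The correlation rho between baseline and follow-up fat; the ratio of the two SDs; the correlation r of baseline fat with change; and the correlation of baseline fat with adherence.

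**Step 1: variance of change explained by baseline.** With equal SDs, r² = (1 − rho)/2. If adherence and the other covariates are unrelated to baseline fat, the SE is multiplied by √(1 − r²). A coefficient tested at 80% power without baseline would then have power Φ((1.96 + 0.842)/√(1 − r²) − 1.96). The 80% is only a reference point, because the protocol sets no power here.

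| rho | r² | SE reduction | 80% power becomes |
|---|---|---|---|
| 0.3 | 0.35 | 19% | 94% |
| 0.5 | 0.25 | 13% | 90% |
| 0.7 | 0.15 | 8% | 86% |
| 0.8 | 0.10 | 5% | 84% |
| 0.9 | 0.05 | 3% | 82% |

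If the SD shrinks on the diet, the gain is larger. With follow-up SD at 0.6 of baseline and rho 0.5, the covariance of change with baseline is 0.30 − 1 = −0.70 and the variance of change is 0.36 + 1 − 0.60 = 0.76. Hence r = −0.70/√0.76 = −0.80 and r² = 0.64.

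These are shares of the raw variance of change. Age, weight change and contraceptive use are already in the model. If baseline fat is related to weight loss, part of the gain has already been taken.

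**Step 2: simulation of the adherence model.** n = 51, 1,500 runs per setting, SD units. Covariates were age, contraceptive use, weight change (correlated −0.4 with adherence) and adherence, with a true adherence effect of 0.30 in size. With adherence unrelated to baseline fat:

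| size of r (baseline, change) | SE without baseline | SE with baseline | reduction |
|---|---|---|---|
| 0 | 0.161 | 0.163 | none |
| 0.3 | 0.161 | 0.155 | about 4% |
| 0.5 | 0.160 | 0.140 | about 13% |
| 0.7 | 0.161 | 0.117 | about 27% |
| 0.8 | 0.161 | 0.098 | about 39% |

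Bias was zero within simulation error in every row, with or without baseline fat.

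**Step 3: bias if adherence is related to baseline fat.** In this set-up, the omission bias is about r(baseline, change) × r(baseline, adherence). For correlations of size 0.3 with adherence, this gives 0.3 × 0.3 = 0.09, 0.5 × 0.3 = 0.15 and 0.8 × 0.3 = 0.24. The simulation gave about 0.09, 0.15 and 0.24 against the true effect of 0.30. For correlations of size 0.1, it gave about 0.02 to 0.03 at r = 0.3 and 0.08 to 0.09 at r = 0.8. With baseline fat in the model, the bias was essentially zero throughout.

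In the setting with both correlations at 0.3, the SE stayed at about 0.16 with or without baseline fat. The benefit there is removal of bias, not precision.

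**The case against.** **The covariate list may not be closed.** The wording need not be exhaustive, and a statistical analysis plan that is not shown could add the baseline value. That is possible. But the protocol does name specific covariates for this outcome, and the one most directly tied to it is missing.

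**Bias is not shown.** A reader might infer that the adherence coefficient is confounded by starting fat. The documents do not support that. It requires an association between starting fat and adherence, on which they give no evidence; without one, the bias is zero. Adherence is also absent from the main liver fat model and enters only the additional analysis. Nor does the omission bias the group's average change. This objection stands, so confounding can be put only as a possibility.

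**The size is assumed.** A reader might also take the power figures as an estimate of what the trial loses. They are not: the starting power is invented, the variance share is the raw one, and the gain becomes small at high rho. This stands too.

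**The scale is unclear.** A change given in (%) could be absolute or relative. The 4% versus 20% illustration applies only to percentage points. Dependence on the starting value is likely on either scale, but the floor argument is weaker for relative change.

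**The fix leaves a larger question open.** Change in body weight is a post-baseline variable and may lie on the path from adherence to fat loss. Even with baseline fat included, the adherence coefficient would not show the whole relation of diet-following to fat loss. This is correct. It limits what the fix achieves, but it is no reason to leave baseline fat out.

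**The subpopulation is small.** About 20 women are planned, so one more covariate costs relatively more there. This is true, but the cost is still a single degree of freedom.

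**Conclusion.** The point holds as a likely loss of precision and a possible source of confounding in a secondary analysis. Section 10.2 fixes covariates for a single-group change score and leaves out the starting value, which must exist for every woman who has an outcome.

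The size cannot be derived from the protocol. Under equal SDs, the variance reduction is 25% at rho 0.5 and 10% at rho 0.8, less whatever weight change already accounts for. The bias in the adherence coefficient ranges from nil, if adherence is unrelated to starting fat, to roughly 0.09 to 0.24 SD for correlations of 0.3 with adherence and 0.3 to 0.8 with change. The weight-change coefficient is exposed in the same way in both analyses.

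No primary conclusion, sample size or safety decision depends on this. It is a worthwhile and nearly free improvement, best made before the data are seen.

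**What to change.** In section 10.2, add T0 liver fat content (%) as an independent variable in the liver fat model and in its additional analysis with adherence. Make the same change in the subpopulation versions, and state whether change is in percentage points or relative to baseline.

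No new scans or measurements are needed, and no woman is lost: anyone without a T0 value already has no change score.

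The cost is one degree of freedom. With 51 women, the adherence model has an intercept and four covariates, so residual degrees of freedom go from 46 to 45. With 20 women in the subpopulation (no contraceptive term), they go from 16 to 15. If baseline fat turns out to be unrelated to change, the simulated SE rises only from 0.161 to 0.163, or from 0.162 to 0.170 when it correlates 0.3 with adherence.

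Whether to keep change in body weight in a model meant to describe adherence is a separate decision that this change does not settle.

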8.3 Study procedures

Standard procedure / current best clinical practice

Main study population

Subjects present themselves at our outpatient clinic after referral from a peripheral or other tertiary/university hospital. Subjects will be receiving additional imaging studies (f.i. an MRI) if the necessary imaging study has not been conducted at the peripheral/referring hospital, according to current standard protocol/clinical practice. Afterwards their case will be discussed in our multidisciplinary meeting, including a (liver) radiologist, hepatobiliary surgeon, gastroenterologist / hepatologist and dietician.

During current clinical practice, subjects will enter the "Wait and See" / "Active Surveillance" period for 6 months (30) based on several criteria. See figure 1 for the management flowchart.

Subpopulation

Subjects eligible for inclusion into the study subpopulation are already being treated via the outpatient clinic via active surveillance. After the initial 6 months of active surveillance (with advice consisting of cessation of use of oral contraceptives and aiming for weight loss), subjects have been subjected to an MRI. If this MRI shows no or only a minimal (5mm) reduction of the size of the HCA, patients are subjected to another active surveillance period of 6 months after which another MRI is performed. We want to provide the patients with the option to adhere to the ketogenic diet as a potential therapeutic option.

Intervention / Study procedure

Time of inclusion:

Eligible subjects visiting the outpatient clinic after discussion of their case in the multidisciplinary meeting are invited to participate in the study. The possible participant is asked whether she wants to be approached for further information on this study. The gastro-enterologist / hepato-biliary surgeon shortly explains the purpose of the study after which, if the subject agrees to it, the study investigator explains the study design and purpose in more detail. Subjects receive written information and are offered a reflection period of one week before they are contacted again about participation in the study. In case informed consent is given, subjects will receive an appointment with a dietician.

Follow-up and outpatient visits will be identical to normal procedure, except the extra appointments with the dietician and the additional blood samples drawn by venous puncture on T₀, T₃ and T₅.

Consultation by Dietician

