10. STATISTICAL ANALYSIS

Categorical data will be presented as numbers (percentage) and continuous variables as mean (standard deviation/normal distribution) or median (interquartile range/no normal distribution).

An Intention-to-treat analysis will be conducted to account for the feasibility of the caloric restricted and ketogenic diet. A two-sided significance level of 0.05 will be used for all primary and secondary analyses unless stated otherwise.

Statistics will be computed using IBM SPSS software version 21.0 (Chicago, IL) or R version 4.0.2 or newer.

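### Plasma changes get a two-time-point test although blood is drawn at three visits and the protocol already plans a mixed-effects model for other outcomes at those visits (minor, cheap to improve)

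*Protocol*

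**What the plan says.** For the plasma panel, Protocol section 10.2 states: "Changes in plasma parameters will be compared in our intervention group by using descriptive statistics, t-test in the case of continuous outcome variables with normal" (the sentence continues). A non-parametric test is used when normality fails, and a Chi-square test for categorical data. The section does not say whether the test is paired or which draws are compared.

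The sampling schedule is in section 8.3: "Blood sampling will be done thrice, each time 2 tubes of 10ml will be withdrawn", with "the additional blood samples drawn by venous puncture on T₀, T₃ and T₅". The study overview table in that section puts laboratory testing, anthropometric measurements, nutritional assessment and RAND-36 all at T0, T3 and T5.

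In section 10.2, weight, body composition and resting energy expenditure "will be estimated in our intervention group by a mixed-effects model analysis, taking repeated measurements into account". Quality of life gets the same type of model. No reason is given for treating plasma differently.

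Four other statements bear on the point:
- Section 10: "An Intention-to-treat analysis will be conducted to account for the feasibility of the caloric restricted and ketogenic diet".
- Section 4.4: "Anticipating +/- 10% drop-out, we aim to include 55 participants in this study".
- Section 8.5 replaces women who opt out.
- Section 8.6 keeps women who do not complete the diet in follow-up.

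**The concern.** A t-test or its non-parametric counterpart handles one pair of time points. Applied to within-woman change from T0 to T5, it needs both values from each woman. A woman who gives blood at T0 and T3 and then leaves the study adds nothing to that comparison, although her 3-month value says something about where she would have been at 6 months. A repeated-measures model uses that value.

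Insulin, IGF-1 and β-hydroxybutyrate carry the mechanism proposed in the protocol's introduction. No plasma comparison with the historical controls is planned, so the within-group change is the whole result. If women with a weak 3-month response leave more often, the women left at T5 look somewhat better than those who started. The plasma results would also rest on a slightly different set of women from the weight and body-composition results beside which they are read.

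**Working it through.** **1. Method set against schedule.**

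| Outcome | Visits (8.3) | Method (10.2) |
|---|---|---|
| Plasma parameters | T0, T3, T5 | t-test or non-parametric test |
| Weight, body composition, resting energy expenditure | T0, T3, T5 | mixed-effects model |
| Quality of life (RAND-36) | T0, T3, T5 | mixed-effects model |

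**2. Inputs.** From section 4.4: 55 women and about 10% drop-out, so 55 × 0.10 = 5.5, or five to six women. The protocol gives no plasma effect, SD, correlation or drop-out timing. The sample-size figure of 51 concerns tumour diameter, so there is no plan figure to reproduce here. The following are assumptions:
- All loss falls after the T3 draw.
- The correlation r between the 3-month and 6-month changes is 0.5 to 0.8.
- Leaving depends on the standardised 3-month change x through P(leave) = 1/(1 + exp(−(a − b·x))), with a set so that 10% leave.

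**3. Formula.** In SD units of the 6-month change, bias of the mean among women with both samples = r × E[x | stays].

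**4. Numbers at 10% loss** (E[x | stays] by numerical integration).
- Odds of leaving double per SD of worse response (b = ln 2 = 0.693): E[x | stays] = 0.066. Bias is 0.5 × 0.066 = 0.033 to 0.8 × 0.066 = 0.053.
- Steeper rule (b = 1.2; odds × exp(1.2) = 3.3 per SD): E[x | stays] = 0.105. Bias is 0.5 × 0.105 = 0.052. With r = 0.8 it would be 0.8 × 0.105 = 0.084.
- Bounding case, in which exactly the worst 10% at 3 months leave: E[x | stays] = φ(1.2816)/0.90 = 0.1755/0.90 = 0.195. Bias is 0.5 × 0.195 = 0.10 to 0.8 × 0.195 = 0.16.
- Leaving unrelated to response (b = 0): bias is 0.

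**5. Simulation check** (n = 55, 10% loss after T3, correlation 0.7 between any two visits, which implies r = 0.5). The mean change in women with both samples was biased by 0.032 SD at b = 0.693 and 0.053 SD at b = 1.2. The likelihood estimate from all three draws was unbiased to within simulation error. With random leaving both were unbiased, and the all-sample SE was about 1% smaller (roughly 0.140 against 0.142).

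**6. Scale.** The SE of a mean change with about 50 women is 1/√50 = 0.14 SD. A bias of 0.03-0.05 is therefore 0.03/0.14 = 0.21 to 0.05/0.14 = 0.36 of one SE. Relative to a true change of 0.5 SD it is 6-10%; relative to a true change of 1 SD it is 3-5%. With no true change, the two-sided 5% test rejects about 6-7% of the time under the two selective rules.

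**The case against.** The strongest reply is that much of the problem has to be inferred. A reader might take section 10.2 to prescribe a completers-only analysis. It does not: it mentions neither completers nor pairing and names no draws. It also leaves room for separate T0-T3 and T0-T5 tests, in which a woman who leaves after T3 still counts at T3. Handling of missing values is commonly settled in the statistical analysis plan, so silence on it is no finding. This stands. What remains is that the named test, used for the T0-T5 change, cannot draw on the T3 value.

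A reader might also infer a contradiction with the intention-to-treat statement in section 10. That link is weak. The statement is tied to feasibility of the diet, meaning that women are analysed whatever their adherence, and section 8.6 supports it by retaining women who stop the diet. The women most likely to respond poorly, those who cannot keep to the diet, are therefore not lost merely for stopping it. Only women who leave the study are lost, and nothing in the protocol ties leaving to a small plasma response. Replacement of opt-outs under section 8.5 adds new women but does not recover the values of those who left.

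Finally, the percentage overstatement depends on the assumed effect. The absolute bias is nearly constant, and the introduction expects plasma changes on such a diet to be potentially large, which makes the relative bias smaller. A higher rejection rate when a true change exists is not evidence of false positives; with no true change the excess over 5% is one or two percentage points.

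**Conclusion.** The point holds as a minor improvement. Section 10.2 fixes a two-time-point test for a three-visit outcome and departs, without a reason, from the method it uses for other outcomes at the same visits. The consequence is conditional and small. At 10% drop-out the T0-T5 change can be overstated by about 0.03-0.05 SD of change if leaving follows a poor 3-month response. It can be more, up to 0.10-0.16 SD, only under steeper or extreme selection. It is zero if leaving is unrelated to response. The documents do not support saying that the change will be overstated.

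The size rests on assumed correlations, assumed selection and loss placed after T3. That timing favours the model: women who leave before T3 have only a baseline sample, and the model recovers little for them. The outcome is secondary and uncontrolled in a proof-of-concept study, and neither the primary endpoint nor the sample size depends on it.

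**What to change.** In section 10.2, replace the t-test and non-parametric rule for continuous plasma parameters with the following specification:
- A mixed-effects model for each parameter, with visit (T0, T3, T5) as a categorical fixed effect and a within-woman covariance structure or random intercept.
- Every available sample from all women who started the diet.
- Log transformation of right-skewed parameters.
- T0-T5 as the main contrast and T0-T3 as supportive.

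Do not copy the body-weight model unchanged: it lists sex as a covariate, and section 4.1 admits only female subjects, so a sex effect cannot be estimated. Leave the Chi-square rule in place for any categorical data.

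The cost is a small text change, with no extra samples, visits or software. On the downside, log-transformed results are reported as ratios, the model assumes that missing samples are explained by the observed values, and women with only a T0 sample add little.
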